9. ADVERSE EVENT RECORDING AND REPORTING

9.1 Recording Requirements

- Research subjects will be routinely questioned about treatment related adverse events at each study visit. All possible, if any, non-serious examples are pain, erythema/redness, skin thinning/atrophy, infection, color/texture change, swelling, telangiectasia, graft shrinkage/rejection and need for additional surgery. Serious adverse events are not expected to be seen at any moment of the study since medication has been shown to be safe to the patient. In addition, patients will be evaluated for early post-operative complications (within 2 weeks of surgery) not related to study drug treatment. Example of that are wound dehiscence, graft necrosis, infection, bleeding, partial/complete graft failure and/or ectropion. Events will be followed until it resolves or stabilizes; if needed other treatment (eg. antibiotics) will be added to manage adverse event.

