9.3 Withdrawal of Subjects due to Adverse Events

- If subject presents with a serious event from intervention, he/she will be withdrawn from further study intervention and the investigators will evaluate the reason for event. If patient states a minor adverse event patient will continue unless patient wishes to voluntary withdraw.
- A serious event includes a severe allergic reaction to medication causing systemic symptoms of anaphylaxis.
- Data will continue to be collected from the withdrawn subjects, until 12 months after original surgery date, but without further intervention (no more injections) and patient will not be included in the analysis.

Withdrawn subjects from study participation due to an adverse event will not be replaced for a new patient.

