13. STUDY DISCONTINUATION CRITERIA

13.1 Discontinuation of Individual Research Subjects

- Discontinuation criteria for individual research subjects has been previously addressed under section 5.2 (Withdrawal of subjects due to non-compliance/adherence) and section 9.3 (Withdrawal of subjects due to adverse events) of the clinical protocol. Decision will be done by PI. Data will be collected until subjects are withdrawn. If subjects have already received part of the treatment or withdrawn before treatment has been started then subjects will be replaced using the same eligibility criteria.

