### 10.4 Analysis Population (if applicable)

- Independent sample t-test will be applied to the primary outcome analysis (i.e., comparison of mean changes in graft size from pre-treatment to the last follow up). In addition, for the secondary outcome we will utilize repeatedly measured POSAS scores over time by using longitudinal linear mixed effects model which can further determine the time dependency of the treatment effect. The model will include treatment group (group 0 for placebo and 1 for treatment), time (0=two-three weeks post-op visit / first injection, 1=second injection, 2=third injection, 3=fourth injection, 4=two to three weeks after last injection), and group x time. Both effects (1. group difference in the pre-treatment measurement 2. time trend of the control) will be considered fixed effects and the individual 2-3 weeks post-operative measurement random. Group x time effect is expected to be an increased slope of the treatment group over time. For the other outcome measurements, we will apply the same methods. Also statistical methods will include intention to treat (ITT) analysis to compare all subjects in the groups randomly assigned. We will exclude anyone who gets partial treatment, exit early or is lost to follow up; in those cases we will replace patient with another subject that meets the criteria. Discussed with [name] at MGH biostatistics.

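### SAP 10.4 does not fix the primary analysis set: it promises intention-to-treat, then excludes and replaces patients who do not complete

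*SAP*

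**What the plan says.** Two consecutive sentences in SAP 10.4 set out who is analysed. The first says that "statistical methods will include intention to treat (ITT) analysis to compare all subjects in the groups randomly assigned". The second says "We will exclude anyone who gets partial treatment, exit early or is lost to follow up; in those cases we will replace patient". Neither is tied to a named analysis. SAP 10.5 repeats that a t-test will be used but names no set of patients. SAP 10.3 allows analysis to begin when 10 patients per arm have finished the study.

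Protocol 9.3 deals with withdrawal for adverse events. Such patients are still followed up to the 12-month point, "but without further intervention (no more injections) and patient will not be included in the analysis". It adds: "Withdrawn subjects from study participation due to an adverse event will not be replaced for a new patient".

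The other replacement rules differ:
- Protocol 5.2 replaces non-compliant patients and says that the replacement gets the medication that corresponds.
- Protocol 13.1 replaces patients withdrawn before or during treatment, and collects data only up to withdrawal.
- SAP 10.4 replaces partly treated patients with no exception for adverse events.

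Protocol 1.2 and 3.1 allow up to four injections, while 5.1 gives a total of 4. Protocol 7.7 and 8.1 let the physician withhold an injection because of an adverse event such as infection.

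**The concern.** The set of patients in the primary test has to be settled before any outcome is seen. Here two analysts could take different sets from the same section, report different primary results, and each cite the SAP. With 10 to 15 patients per arm, a few inclusions or exclusions matter.

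If the exclusion is applied, randomisation no longer protects the comparison. Whether a patient counts then depends on what happened after allocation, and that can be related to treatment. A patient whose injection is withheld for an infection has had partial treatment and could be dropped on that ground, without any serious event. Because the planned number of injections is stated in two ways, partial treatment has no clear threshold, and the decision could be made late. No missing-data method is given for those who leave.

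**Working it through.** **The plan's own figure.** Inputs from SAP 10.3: difference 13.2 points, SD 10, two-sided alpha 0.050, equal-variance t-test. With noncentrality 13.2 / (10 × √(2/n)), power is 79.7% at n = 10 per arm, 87.1% at 12 and 93.7% at 15. The stated total of 20 for 80% power reproduces. The sample size is not the defect.

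**The text, applied to one patient.** Take a randomised patient who has two injections and returns for the last follow-up.
- Under the intention-to-treat sentence, the patient is analysed in the assigned arm.
- Under the exclusion sentence, the patient is left out and replaced.
- If the injections stopped through withdrawal for an adverse event, Protocol 9.3 collects the data to 12 months, leaves the patient out of the analysis and does not replace the patient. SAP 10.4 would replace.

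**Possible size of completer bias (illustration only).** Assumptions not in the documents: no true effect, leavers replaced, and a latent exit score with correlation r to shrinkage, truncated at the loss quantile z. The shift in an arm's mean is 10 × r × φ(z) / (1 − loss):
- 20% loss: 10 × 0.280 / 0.8 = 3.50, so 3.50r.
- 10% loss: 10 × 0.1755 / 0.9 = 1.95, so 1.95r.

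The bias is the difference between the arms' shifts. Type I error was simulated at 10, 12 and 15 per arm.

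| Loss, arm A v arm B | r, A v B | Bias (points) | Type I error |
|---|---|---|---|
| 20% v 20% | 0.3 v 0.3, or 0.5 v 0.5 | 0 | about 5% |
| 20% v 20% | 0.5 v 0.3 | 0.70 | 5.2–5.4% |
| 20% v 20% | 0.3 v 0 | 1.05 | 5.5–5.9% |
| 20% v 20% | 0.5 v 0 | 1.75 | 6.6–7.7% |
| 20% v 10% | 0.3 v 0.3 | 0.47 | 5.1–5.3% |
| 20% v 10% | 0.5 v 0.5 | 0.78 | 5.3–5.5% |
| 20% v 0% | 0.3 in A | 1.05 | 5.6–5.9% |
| 20% v 0% | 0.5 in A | 1.75 | 6.6–7.7% |
| 20% v 10% | 0.3 v 0.54 | 1.05 − 1.05 = 0 | about 5% |

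The last row shows that unequal loss and unequal correlation can cancel. The 1.75 points are the largest of these cases, not a ceiling. With 20% lost from one arm only, they mean a gap of 1.75 / 0.20 = 8.75 points between leavers and completers. A gap of 20 points would give 0.20 × 20 = 4 points and an error of 13.5% (10 per arm) to 18.5% (15 per arm).

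**Power cost of analysing everyone.** Assume that 20% of treated patients gain nothing. The difference becomes 13.2 × 0.8 = 10.56.
- All 15 per arm observed: 79.7% with SD held at 10. The treated arm is then a mixture, with SD √(100 + 13.2² × 0.2 × 0.8) = 11.3; simulating this gives about 74%.
- 12 per arm observed, loss unrelated to non-benefit: 69.6%, or about 64% with the mixture.
- 12 per arm observed, and the treated patients lost are those who did not benefit: the observed difference stays at 13.2 and power is up to 87.1%.

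**The case against.** The best defence is that the SAP says only that the methods include intention-to-treat. It could then be run beside a completer analysis, and both sentences could be followed. That reading is fair, so a reader should not infer that the two sentences are impossible to apply together. It does not remove the defect. The SAP never says which set is primary, defines no completer or per-protocol set, and does not confine the exclusion to a secondary analysis.

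A reader might also infer that the completer comparison must be biased, with a type I error above 5%. The documents do not support that. There is no bias if exit is unrelated to outcome, if loss and its relation to outcome are the same in both arms, or if differing effects happen to cancel. Masking with identical syringes (Protocol 3.1 and 3.2.2) makes arm-specific exit less likely, though it cannot exclude it. The illustrated biases are small beside 13.2 points.

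It can be said that Protocol 9.3 will affect few patients, because "Serious adverse events are not expected to be seen at any moment of the study". That covers serious events only. Section 9.3 also lets a patient with a minor event withdraw voluntarily, and its non-replacement sentence covers adverse events in general, so the number affected cannot be derived.

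Finally, 9.3 and 13.1 need not be a flat contradiction. Section 13.1 says "Discontinuation criteria for individual research subjects has been previously addressed under section 5.2" and goes on to cite 9.3, so 9.3 can be read as the specific rule for adverse events. SAP 10.4 has no such exception.

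**Conclusion.** The concern holds as a defect in the definition of the primary analysis set. Intention-to-treat is promised, an unrestricted exclusion follows, and Protocol 9.3 and SAP 10.3 lean towards completers. If the exclusion is followed, the primary t-test compares completers and their replacements. It can then be biased, and its type I error can exceed 5%, when exit relates to outcome differently in the two arms.

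The documents give neither the size nor the direction. With 20% loss and r up to 0.5 the effect is modest, at most about 1.75 points and 6.6–7.7% error. These values are assumed. The case for changing the text rests on the unidentified primary set, not on these figures.

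**What to change.** - In SAP 10.4, delete the exclusion sentence or relabel it as describing a sensitivity analysis. In Protocol 9.3, delete the clause that leaves withdrawn patients out of the analysis.
- State that the primary t-test includes every randomised patient in the assigned arm, whatever number of injections was received, and uses all graft measurements obtained. Pre-specify how a missing last follow-up measurement is handled. A mixed model on graft size is possible, but it would replace the t-test for which SAP 10.3 was powered.
- Label the completers' comparison as a sensitivity analysis and define partial treatment for it. The injection counts in Protocol 1.2, 3.1 and 5.1 must be reconciled first.
- State that a patient enrolled after a withdrawal is newly randomised and does not displace the withdrawn patient in the analysis. Protocol 5.2 can be read as passing on the arm.
- Reconcile the replacement rules in Protocol 5.2, 9.3 and 13.1 and SAP 10.4, and the data-collection rules in 9.3 (to 12 months) and 13.1 (until withdrawal).

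**Cost.** SAP wording and a short protocol amendment. Grafts are already measured at each visit after surgery (Protocol 8.2), and a case report form is kept for every enrolled patient (12.1). Follow-up after withdrawal for reasons other than adverse events would be new under 13.1, and depends on the patient's agreement. Dilution can lower power. If 20% of treated patients gain nothing, it is about 74–80% with all 15 per arm observed, instead of 93.7%. With 12 per arm observed it ranges from about 64–70% up to 87.1%, depending on who is lost.

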#### **10.5 Effectiveness Analysis (if applicable)**

- As described above, the population analysis that will be employed in the primary and secondary endpoints is a sample t-test with a level of significance of 0.050.

#### **10.6 Safety Analysis**

- The safety analysis of the study drug is our secondary endpoint that will be analyze with a sample t-test using a level of significance of 0.050.

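### Safety is to be tested with a t-test in an undefined population, and section 9.3 read literally removes patients with a serious treatment-caused event from the analysis

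*SAP*

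**What the plan says.** The safety endpoints are treatment-related adverse events and early post-operative complications (SAP 10.2). SAP 10.6 gives the whole safety analysis: "The safety analysis of the study drug is our secondary endpoint that will be analyze with a sample t-test", at a significance level of 0.050. Neither document defines a safety or as-treated population.

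Three other places bear on who is counted:

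- **Protocol 9.3.** "If subject presents with a serious event from intervention, he/she will be withdrawn from further study intervention". Data collection goes on to 12 months after surgery, but the "patient will not be included in the analysis". For lesser events: "If patient states a minor adverse event patient will continue unless patient wishes to voluntary withdraw". On replacement: "Withdrawn subjects from study participation due to an adverse event will not be replaced for a new patient".
- **SAP 10.4.** It promises an "intention to treat (ITT) analysis to compare all subjects in the groups randomly assigned". The next sentence says: "We will exclude anyone who gets partial treatment, exit early or is lost to follow up", and has those patients replaced. On endpoints other than graft size and POSAS: "For the other outcome measurements, we will apply the same methods".
- **Protocol 7.7 and 8.1.** The physician may withhold injections because of an adverse event, with infection as the example.

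Protocol 13.1 says data are collected up to withdrawal and that partly treated patients are replaced.

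**The concern.** An exclusion triggered by an adverse event selects patients on the outcome that the safety analysis is meant to measure. Under 9.3 the link is direct: the serious event causes the withdrawal, and the withdrawal takes the patient out of the analysis. Under 10.4 it is indirect: a withheld injection may count as partial treatment, and a patient who leaves after a minor event has exited early.

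The trial is small, with up to 15 patients per arm and analysis allowed at 10 completers per arm (SAP 10.3). One or two lost patients can turn a non-zero event rate into zero. With no interval specified, a zero could be reported as evidence of safety that this sample cannot supply. A t-test p-value does not give the event rate in either arm.

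**Working it through.** **Inputs.** The arm sizes of 10 and 15 come from SAP 10.3. The documents give no adverse event rate, and Protocol 9.1 expects no serious events, so every event count below is an assumption. The plan states no safety figure to reproduce.

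**1. Effect of 9.3 read literally.** Suppose x of 15 patients on 5-FU have a serious event from the intervention. All treated patients give x/15. Removing those x patients gives 0/(15 − x). Intervals are exact (Clopper-Pearson) 95%. For zero events the upper limit is 1 − 0.025^(1/n).

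| Assumed events | All treated patients | After the 9.3 exclusion |
|---|---|---|
| 1 | 1/15 = 6.7% (0.2% to 31.9%) | 0/14 = 0% (upper limit 23.2%) |
| 2 | 2/15 = 13.3% (1.7% to 40.5%) | 0/13 = 0% (upper limit 24.7%) |
| 3 | 3/15 = 20.0% (4.3% to 48.1%) | 0/12 = 0% (upper limit 26.5%) |

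The observed rate is zero each time, by construction. For one event against 0/15 on placebo, the risk difference moves from 6.7 points (Newcombe 95% CI −14.4 to 29.8) to 0.0 (−20.4 to 21.5).

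**2. What a true zero would show.** 0/15 has an upper limit of 1 − 0.025^(1/15) = 21.8%. 0/10 has 1 − 0.025^(1/10) = 30.8%.

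**3. Whether the bias between arms has a known direction.** Let p be the true event rate in an arm, q the share of event patients excluded and s the share of event-free patients excluded. The analysed rate is p(1 − q) / [p(1 − q) + (1 − p)(1 − s)]. Take assumed true rates of 20% on 5-FU and 5% on placebo, a true difference of 15.0 points:

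| q, 5-FU / placebo | s, both arms | Analysed rates | Difference (points) |
|---|---|---|---|
| 50% / 50% | 0% | 11.1% v 2.6% | 8.5 |
| 50% / 50% | 20% | 13.5% v 3.2% | 10.3 |
| 25% / 25% | 0% | 15.8% v 3.8% | 12.0 |
| 25% / 25% | 20% | 19.0% v 4.7% | 14.3 |
| 20% / 20% | 20% | 20.0% v 5.0% | 15.0 |
| 0% / 50% | 0% | 20.0% v 2.6% | 17.4 |

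All the q and s values are assumptions; s = 20% borrows the overall dropout allowance in SAP 10.3. The difference can shrink, stay the same or grow.

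**4. The t-test on yes/no data.** Take 4/15 v 0/15. The arm variances are 0.2667 × 0.7333 × 15/14 = 0.2095 and 0, so the pooled variance is 0.1048. The standard error is √(0.1048 × 2/15) = 0.118, t = 0.2667/0.118 = 2.26 on 28 df, and p = 0.032. Fisher's exact two-sided p is 2 × C(15,4)/C(30,4) = 2 × 1365/27405 = 0.100. For 4/10 v 0/10 the p-values are 0.025 and 0.087. Exact enumeration over a common event rate gives a maximum t-test size of 4.2% (10 per arm), 6.4% (12) and 5.5% (15).

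**5. Timing of the second safety endpoint.** Early complications are those within 2 weeks of surgery (Protocol 2.2, 9.1). The first injection comes 2 to 3 weeks after surgery (Protocol 1.2, 7.2, 7.8). A set defined by having had an injection would miss most of these events, and also any patient whose complication prevented the first injection.

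**The case against.** The best defence is that the analysis in 9.3 means effectiveness. The protocol keeps collecting data from these patients for 12 months, which makes little sense if they are to be ignored, and 10.4 promises ITT. That reading is possible, and under it the loss in step 1 does not occur. But neither document states it. The ITT promise is contradicted by the sentence after it, and 10.4 extends its methods to the other outcomes.

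Other limits stand. Patients with minor events who continue remain in the analysis. Serious events are not expected. Serious, unexpected, related events still reach the Human Studies Committee (Protocol 9.2), although that is not a comparison by arm. Some of the conflicts are soft: 13.1 refers back to 9.3, so 9.3 can be taken as the specific rule. Whether a withheld injection is partial treatment is also open, since Protocol 1.2 and 3.1 allow up to four injections while 5.1 gives four as the total.

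A reader might infer that the exclusions must make 5-FU look safer relative to placebo. The documents do not support that: step 3 shows that the direction depends on exclusion shares by arm, which they do not give. Nor does the t-test produce serious alpha inflation, since its maximum size stays near 5%.

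**Conclusion.** The plan is wrong as written. It applies a t-test to event data in an unnamed population, while 9.3 literally removes the patients whose serious events matter most. Any serious event that triggers 9.3 then drops out of the reported rate, as in 1/15 becoming 0/14. This rests on the literal reading of 9.3 and on assumed counts. The 10.4 route is real but conditional on what counts as partial treatment and on who chooses to leave.

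No size or sign can be put on the bias in the between-arm difference. The method fault is smaller: the t-test gives no rate or interval per arm and can disagree with an exact test at this sample size. Intervals are needed whichever reading is right, because zero events is compatible with a true rate of up to 21.8% (n = 15) or 30.8% (n = 10). The plan should be changed on this point. Confidence is medium, because an effectiveness-only intent cannot be ruled out.

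**What to change.** - **9.3 and 10.4:** state that the exclusions do not apply to safety.
- **10.6, adverse events:** analyse treatment-related adverse events in all randomised patients who received at least one injection, by treatment received. Include those withdrawn, partly treated or replaced, and use all data recorded.
- **10.6, early complications:** report these separately in all enrolled patients who had surgery, by arm where randomised.
- **10.5 and 10.6, method for events:** replace the t-test with the number and percent of patients per arm, exact 95% intervals, and the risk difference with its interval. Any test should be exact and supportive only.
- **9.3, 10.4 and 13.1:** reconcile the rules on replacement and on data collection after withdrawal.

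The cost is a short amendment. Patients withdrawn for an adverse event need no new visits, because 9.3 already follows them to 12 months; for others, what was recorded is used. The drawback is that the intervals will be visibly wide.

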1.2 Rationale

- There have been two retrospective studies that have investigated the safety and efficacy of 5-FU injected in periorbital skin grafts with or without Kenalog. The first (Massry 2011) used post-operative injections of a 50:50 mixture of 5-FU and triamcinolone for correction of medial canthal webs. In 2 patients, they found it to be safe and effective. The author noted he has used it previously for other scar management cases and was “very pleased with the results and [had] negligible side-effect[s].” The same author performed another study using 5-FU for skin grafts. This study evaluated 19 patients who had skin grafts for various purposes and were injected following surgery (similar to our protocol). This study demonstrated safety of the injection, with no cases of complication. The author concluded that the 5-FU is effective with “minimal scarring, high patient and surgeon satisfaction, and few complications
- Medication will be injected in the periocular skin graft area 2-3 weeks after surgery. The medication will be injected every 2-3 weeks for a total of up to four injections. Concentration of medication is 50mg/ml. Medication will be administered using a 1cc syringe with a 30gauge needle.

- Any competent patient (male or female) from the age of 18 to 89 that presents with any periocular pathology that requires skin graft for reconstruction and consents to participate will be a candidate to be included in the study.
- To your knowledge 5-FU hasn't been withdrawn from research or market in any country for any reason related to its safety or effectiveness.

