### 10.3 Sample Size Determination

- The plan number of subjects to be enrolled into the clinical study is up to 15 for the treatment group and up to 15 for the placebo group. A total sample size of 20 patients is needed to achieve a 80% power to detect a difference of at least 13.2% less than the control in mean changes in graft size from pre-treatment (2-3 weeks post-operative date) to the last follow up with a standard deviation of 10% (common to both groups) and with a significant level (alpha) of 0.050 using a two-sided two-sample equal-variance t-test. If we take into account a 20% dropout rate out of 20 patients, then 12 patients are needed to be enrolled into each arm of the study. For that reason, 15 patients are going to be enrolled but statistical analysis can be done once 10 patients in each arm have completed the study. Determined with the help of [name] at MGH biostatistics department.

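### Safety is analysed only by a t-test at 0.050, so with 10 to 15 patients per arm the plan has no output that bounds harm

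*SAP*

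**What the plan says.** Treatment-related adverse events and early post-operative complications are secondary objectives (Protocol 2.2) and secondary endpoints (SAP 10.2). Their analysis is set out in SAP 10.6, at level 0.050, as follows: "The safety analysis of the study drug is our secondary endpoint that will be analyze with a sample t-test using a level of significance of". SAP 10.5 repeats the t-test at that level for primary and secondary endpoints. SAP 10.4 extends its methods, a t-test and a mixed model, to the remaining outcomes. None of these sections mentions event counts or proportions by arm, a confidence interval, a margin, or how a non-significant safety result would be read.

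The sample size in SAP 10.3 concerns graft size alone: "A total sample size of 20 patients is needed to achieve a 80% power" for a 13.2% difference with a standard deviation of 10%, "using a two-sided two-sample equal-variance t-test". Enrolment is "up to 15 for the treatment group and up to 15 for the placebo group", and "statistical analysis can be done once 10 patients in each arm have completed the study".

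**The concern.** A test of no difference can give evidence of harm. When it is not significant it says little, unless the trial was large enough to find the harm that matters or the result comes with an interval. Here the arms were sized for a very large effect on a different endpoint, and no interval is planned.

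The listed events include infection, skin thinning and atrophy. If 5-FU causes a moderate excess of such events, the trial would probably report no significant difference from saline. The data would leave the safety question open, and nothing in the planned output would show how open.

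**Working it through.** **Inputs from the documents.** Alpha is 0.050 (SAP 10.6). The test is two-sided; this is stated in SAP 10.3 for graft size and carried over, because 10.6 does not state sidedness. There are 10 per arm at the earliest analysis and at most 15 per arm (SAP 10.3).

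**Assumptions.** No safety effect size, event rate or margin is given. I use a 0.5-SD harm with a range of 0.3 to 1.32 SD. For events I use 10% on saline against 30% on 5-FU, which is 0.20/√((0.09 + 0.21)/2) = 0.52 SD.

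**Step 1: reproduce the plan's figure.** The standardised effect is d = 13.2/10 = 1.32. With n per arm, power comes from the noncentral t distribution with 2n − 2 degrees of freedom and noncentrality d√(n/2). At n = 10, the noncentrality is 1.32 × √5 = 2.95 and power is 79.7%. The stated 80% is confirmed, for graft size.

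**Step 2: the same formula for a safety difference.** At d = 0.5 the noncentrality is 0.5 × √5 = 1.12 for n = 10 and 0.5 × √7.5 = 1.37 for n = 15. Power is 18.5% and 26.2%. Miss rates (1 − power) over the range are:

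| True harm | Missed, n = 10 | Missed, n = 15 |
|---|---|---|
| 0.3 SD | 90% | 88% |
| 0.5 SD | 81.5% | 73.8% |
| 0.8 SD | 60% | 44% |
| 1.0 SD | 44% | 25% |
| 1.32 SD | 20% | 6% |

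A one-sided test at 0.05 misses a 0.5-SD harm 71.5% (n = 10) or 62.1% (n = 15) of the time. Two-sided power reaches 50% at 0.93 SD (n = 10) and 0.74 SD (n = 15). Below those values non-significance is the more likely result. Power of 80% for 0.5 SD would need 64 per arm.

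**Step 3: yes/no events.** Most listed events are present or absent, so I also summed exactly over two binomial distributions and applied the t-test to the 0/1 data.

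| Saline vs 5-FU (assumed) | Missed, n = 10 | Missed, n = 15 |
|---|---|---|
| 10% vs 30% | 86% | 72% |
| 10% vs 40% | 71% | 49% |

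Fisher's exact test misses 10% vs 30% in 94% (n = 10) and 85% (n = 15), so a test better suited to binary data does not remove the problem.

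**Step 4: what the data could bound.** The half-width of the 95% interval for a mean difference is about 0.94 SD at n = 10 and 0.75 SD at n = 15. Even an observed difference of zero would not exclude a 0.5-SD harm. With no events in n treated patients, the upper limit on the event rate is 1 − 0.05^(1/n) (one-sided 95%) or 1 − 0.025^(1/n) (two-sided 95%):

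- n = 15: 18.1% and 21.8%
- n = 10: 25.9% and 30.8%

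**Step 5: an example.** Take 3/15 events on 5-FU and 0/15 on saline. The difference is 0.20. The pooled variance is (3 × 12/15)/28 = 0.0857, the standard error is √(0.0857 × 2/15) = 0.107, and t = 1.87, giving p = 0.07. The Newcombe 95% interval for the excess runs from −4 to +45 percentage points. The planned test returns not significant, whereas the interval shows that a large excess remains possible.

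**The case against.** SAP 10.6 names a method, not a decision rule. A reader might infer that the plan will declare 5-FU safe if p exceeds 0.05. The documents do not say so, and a t-test can be reported with its difference and interval, which 10.6 does not forbid. That objection stands. The fault is that no bound on harm is planned, not that a wrong conclusion is announced.

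A reader might also infer that the protocol already reads a null result as safety, because Protocol 1.2 says "This study demonstrated safety of the injection, with no cases of complication" and Protocol 9.1, referring to the patient, says "Serious adverse events are not expected to be seen at any moment of the study since medication has been shown to be safe to the" […]. The documents do not support this either. Section 1.2 describes a retrospective series and mentions no control arm or significance test, and 9.1 names no source. Section 1.2 also reports the series' author as concluding that complications were few, so a count of none among the 19 patients is not secure enough to calculate from.

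Harm is judged elsewhere without a p-value: early stopping (Protocol 7.7), monthly review (11.1) and discontinuation (13.2). These are qualitative rules for conduct and do not analyse the endpoint.

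Low power for safety is common to trials of this size, and the calculation does not show that every harm would be missed. At 15 per arm, 0.8 SD and 10% vs 40% are each missed less than half the time. The claim is therefore limited to smaller harms. Finally, an upper limit without a margin does not by itself settle whether the drug is safe. That is true, but the limit states which harms remain possible, and the test alone does not.

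**Conclusion.** The point holds as a gap in the planned analysis of a stated secondary objective. At the planned arm sizes, a non-significant safety test could not support a safety conclusion, and nothing else is planned that would limit how large a harm remains possible. Under a two-sided test, an assumed 0.5-SD harm is missed about 82% (10 per arm) or 74% (15 per arm) of the time; one-sided, about 72% or 62%.

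The effect sizes, event rates and sidedness are assumptions for safety. The conclusion that non-significance is the likelier result holds only below about 0.93 SD (10 per arm) or 0.74 SD (15 per arm). The primary endpoint is unaffected. The plan should be changed, but this does not undermine the trial.

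**What to change.** Change SAP 10.6 only, and align the reference to secondary endpoints in 10.5 with it:

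- Replace the lone t-test with counts and proportions of each adverse event by arm, with the denominator shown.
- Give an exact 95% confidence interval for the 5-FU event rate and a 95% confidence interval (for example Newcombe's) for the 5-FU minus saline difference, in percentage points.
- Base the safety statement on the upper limits.
- State that a non-significant difference will not be taken as evidence of safety, and that zero events in 15 treated patients excludes only rates above about 18–22% (26–31% with 10).

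No change to Protocol 1.2 or 9.1 is asked for. The cost is SAP wording, with no added patients, visits or data. The downside is a weaker, explicitly bounded safety claim.
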